## 8.4 Analyses Plans

### 8.4.1 Analysis Population

- The analysis population for the primary outcome will be all subjects with pre- and post-pembrolizumab treatment tumor specimens that are evaluable for TICCs.
- The All Subjects as Treated (APaT) population will be used for the analysis of the secondary endpoints of clinical efficacy (ORR) and safety/toxicity outcomes. The APaT population consists of all subjects who received at least 1 dose of pembrolizumab-based therapy. At least 1 laboratory or vital sign measurement obtained subsequent to at least 1

dose of study treatment is required for inclusion in the analysis of each specific parameter. To assess change from baseline, a baseline measurement is also required.

- Subjects who undergo CN and/or MET will be evaluable for the exploratory clinical efficacy endpoints: pathologic response rate and R0 resection rate
- Additionally, subjects who receive continued pembrolizumab-based therapy will be evaluable for additional exploratory clinical endpoints (DFS/PFS at 1 and 2 years, median DFS and PFS)

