### 2.2.2 Secondary

- The clinical efficacy of preoperative pembrolizumab-based therapy in subjects with advanced RCC will be assessed by ORR, defined as CR or PR per Response Evaluation Criteria in Solid Tumors (RECIST) 1.1, modified to allow a maximum of 10 target lesions or 5 target lesions per organ.
- The clinical efficacy of continued pembrolizumab-based therapy in subjects with advanced RCC will be assessed as follows:
  - In subjects who obtain CR or PR/SD with R0 resection and are treated 1 year of pembrolizumab-based therapy:
    - 1-year and 2-year disease-free survival (DFS) rate, and median DFS
  - In subjects who obtain PR/SD and have residual disease following CN/MET and are treated with 1 year of pembrolizumab-based therapy:
    - 1-year and 2-year PFS rate, and median PFS
- Safety will be assessed and reported using National Cancer Institute (NCI) Common Terminology Criteria for Adverse Events (CTCAE) version 5.0
  - Surgical complications will be assessed according to the Clavien-Dindo classification (Appendix 3)

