- The first dose of study treatment following CN/MET may be no sooner than 3 weeks and no later than 6 weeks following surgery, to allow for postoperative recovery (adequate wound healing and recovery from any postoperative complications) as assessed by the treating surgeon. Subjects who cannot resume therapy within 42 days for any reason will discontinue study participation, any exception will be discussed with the PI and approved on a case-by-case basis.

At the time of disease progression (or death, unacceptable toxicity, or withdrawal of consent, whichever occurs first) on postoperative pembrolizumab-based therapy, subjects will discontinue study participation. Prior to study discontinuation, all subjects will be consented for an additional optional tissue collection.

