### 5.1.4 Continuation of Pembrolizumab-based Therapy Following CN/MET

Following CN/MET, post-operative therapy for patients who achieved pre-operative CR/PR/SD will proceed as follows (see Section 6.3):

- Subjects with an R0 resection (NED, margins negative) or R1 resection (microscopic disease, margins positive) will continue receiving pembrolizumab-based combination therapy (with pembrolizumab dosing as 400 mg Q6W) for up to 9 cycles or until disease progression, death, unacceptable toxicity, or withdrawal of consent, whichever occurs first.

- Subjects with an R2 resection (macroscopic disease after surgery), or who had a pre-operative CR but did not undergo CN, will continue receiving pembrolizumab-based combination therapy (with pembrolizumab dosing as 400 mg Q6W) for up to 18 cycles or until disease progression, death, unacceptable toxicity, or withdrawal of consent, whichever occurs first.
- Subjects will begin their first post-operative treatment no sooner than 21 days and no later than 42 days following CN and/or MET.

All subjects will be consented for optional tissue and blood collection at the time of disease progression.

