#### Secondary endpoints:

- The clinical efficacy of preoperative pembrolizumab-based therapy in subjects with advanced RCC will be assessed by ORR, defined as CR or PR by RECIST 1.1 criteria.
- The clinical efficacy of:
  - Continued pembrolizumab-based therapy will be assessed as follows:
    - In subjects who achieve CR or PR/SD followed by R0 resection: proportion of subjects who remain disease-free at the end of the 1 year continued treatment period (1-year DFS rate), and at 1 year following the end of the continued treatment period (2-year DFS rate), and the median DFS.
    - In subjects who achieve PR/SD with residual disease following CN/MET: proportion of subjects who remain progression-free at the end of the 1 year continued treatment period (1-year PFS rate) and at 1 year following the end of the continued treatment period (2-year PFS rate), and the median PFS.
  - Safety will be assessed and reported using NCI CTCAE version 5.0.
    - Surgical complications using Clavien-Dindo classification (Appendix 3)

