#### **8.4.3 Secondary Analysis (or Analysis of Secondary Endpoints)**

The study will use descriptive statistics to report on the ORR (by RECIST 1.1) following preoperative therapy; DFS/PFS rate at 1-year and 2-years following CN/MET; safety/toxicity of preoperative pembrolizumab-based therapy by NCI CTCAE. Median DFS/PFS following CN/MET will be reported using the Kaplan-Meier estimate.

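### DFS/PFS is limited to subjects who start postoperative therapy but reported from surgery, 3 to 6 weeks earlier, and the plan's sections disagree on time zero

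*Combined protocol and SAP*

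**What the plan says.** **Who is counted.** Section 8.4.1: "subjects who receive continued pembrolizumab-based therapy will be evaluable for additional exploratory clinical endpoints (DFS/PFS at 1 and 2 years, median DFS and PFS".

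**From when.** Section 8.4.3 reports the "DFS/PFS rate at 1-year and 2-years following CN/MET", and adds that "Median DFS/PFS following CN/MET will be reported using the Kaplan-Meier estimate".

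**The gap.** Section 5.1.4: "Subjects will begin their first post-operative treatment no sooner than 21 days and no later than 42 days following CN and/or MET". Section 3.1 gives the same window in weeks: "The first dose of study treatment following CN/MET may be no sooner than 3 weeks and no later than 6 weeks following surgery". It continues: "Subjects who cannot resume therapy within 42 days for any reason will discontinue study participation", with exceptions case by case. Section 6.1.2.6 and the notes to Table 7 repeat the 42-day limit without the exceptions.

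**A competing definition.** The secondary endpoints in 8.1 define the 1-year DFS rate as the "proportion of subjects who remain disease-free at the end of the 1 year continued treatment period (1-year DFS rate". The 2-year rate is taken one year after that, and PFS is worded in parallel. Section 8.1 names no start date and gives no time point for the median.

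No section formally defines time zero for DFS or PFS, and none specifies a landmark, delayed entry or a sensitivity analysis. DFS/PFS is secondary in 2.2.2 and 8.1 but exploratory in 8.4.1.

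**The concern.** Membership of the analysis set is decided by something that happens after surgery, namely receiving a postoperative dose. If the clock starts at surgery, every operated subject in the set has 3 to 6 weeks of follow-up in which an event that prevented the first dose could not have been recorded. A subject who dies of a surgical complication in that window, or progresses clinically and never restarts, is removed instead of being counted as a failure. Both effects push the 1-year rate, the 2-year rate and the median upward, and a larger sample would not remove them.

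The plan itself expects losses in this window. It monitors Clavien-Dindo Grade IV and V complications (Grade V is death), and it ends participation for subjects whose wounds have not healed by day 42.

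A second problem is that a surgery clock gives no start date to some subjects who may continue treatment: metastatic subjects with a preoperative CR who skip surgery (5.1.2.2), and PR/SD subjects for whom surgery proves unsafe or infeasible (3.1).

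**Working it through.** The plan states no assumed DFS/PFS rate, median, event count or precision, so there is no figure of its own to reproduce. The size of the effect has to be illustrated.

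**Inputs**
- Gap g from surgery to first postoperative dose: 21 to 42 days (5.1.4). With 30.4375 days per month, g = 0.69 to 1.38 months.
- Median from surgery: an assumption. 15.1 months is the PFS median of the pembrolizumab plus axitinib trial cited in 1.2.2.1, which was not a post-surgical population. The range 8 to 36 months is also assumed.
- Constant hazard h = ln 2 / median, so S(t) = exp(−ht).
- Every event before the first dose is taken to remove the subject from the set.

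**Formulas**
- Share failing before first dose: 1 − S(g).
- 1-year rate in all operated subjects, counted from surgery: S(12).
- 1-year rate in starters, counted from surgery: S(12)/S(g).
- Median in starters, counted from surgery: median + g, because the hazard is constant.

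**At 15.1 months**
- h = 0.6931/15.1 = 0.0459 per month; S(12) = 57.6%.
- S(0.69) = 96.9% and S(1.38) = 93.9%, so 3.1% to 6.1% fail in the gap.
- Starters from surgery: 0.5765/0.9688 = 59.5%, to 0.5765/0.9386 = 61.4%. The inflation is 1.9 to 3.8 points.
- Median: 15.1 + 0.69 = 15.8, to 15.1 + 1.38 = 16.5 months.

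**Across assumed medians (gap 21 to 42 days)**

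| Median (months) | True 1-year rate | Fail before first dose | 1-year inflation (points) | 2-year inflation (points) |
|---|---|---|---|---|
| 8 | 35.4% | 5.8–11.3% | 2.2–4.5 | 0.8–1.6 |
| 11.1 | 47.3% | 4.2–8.3% | 2.1–4.3 | 1.0–2.0 |
| 15.1 | 57.6% | 3.1–6.1% | 1.9–3.8 | 1.1–2.2 |
| 24 | 70.7% | 2.0–3.9% | 1.4–2.9 | 1.0–2.0 |
| 36 | 79.4% | 1.3–2.6% | 1.1–2.1 | 0.8–1.7 |

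The median is inflated by 0.7 to 1.4 months in every row.

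**Simulation.** With 1,000,000 subjects, a 15.1-month median and start days uniform on 21 to 42, 4.7% are dropped. The 1-year rate is 57.6% in all operated subjects, 60.4% in starters counted from surgery, and 57.6% in starters counted from first dose.

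**How far apart 8.1 and 8.4.3 are.** Nine 42-day cycles last 9 × 42 = 378 days. Adding the gap, the treatment period ends 399 to 420 days after surgery. That is 57 to 60 weeks (13.1 to 13.8 months), not 12 months.

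**Against sampling error.** At a rate of 57.6%, the 95% half-width is 1.96 × √(0.576 × 0.424/n): about 18 points for n = 30 and 28 points for n = 12, before subjects are split into DFS and PFS groups.

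**The case against.** **The surgery clock is not settled.** Section 8.1 places the 1-year rate at the end of the treatment period, roughly a year after the first postoperative dose. The reference to surgery in 8.4.3 could name a study phase and not a clock start. This stands for the rates: the documents conflict, and on the 8.1 reading the rates carry little or no immortal time. It does not help the median, which is described only in 8.4.3, and 8.1 does not bring non-starters back in.

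**Starters are the right set for an objective about continued therapy.** Agreed. The fault lies in pairing that set with a surgery origin.

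**Not every early failure is lost.** A reader might infer that anyone who progresses before the first postoperative dose is excluded. The documents do not support that. Table 7 schedules no scan between week 10 and week 15, and week 15 is the first postoperative dose visit. Sections 7.1 and 7.1.3 allow treatment to continue while progression is verified, and 3.1 allows exceptions to the 42-day limit. The losses to expect are mainly deaths and clinically evident progression, so the modelled figures are an upper range on this point. The constant hazard works the other way: an excess of deaths or failures soon after surgery would enlarge the bias.

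**Complications as such.** A reader might also infer that the bias grows with surgical complications generally. Slow wound healing is not a DFS/PFS event. Excluding those subjects biases the estimate only if they later do worse, and nothing in the documents shows this.

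**Completers only.** Section 2.2.2 words the DFS group as "In subjects who obtain CR or PR/SD with R0 resection and are treated 1 year of pembrolizumab-based therapy". A reader might infer that only subjects who finish a full year are analysed, which would be far more serious. Section 8.4.1 asks for receipt of continued therapy, not completion, and the treatment sections describe the cycles as a maximum that ends at progression. The 2.2.2 phrase is better read as describing the planned course.

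**Conclusion.** The point holds in a limited form. The analysis set in 8.4.1 and the origin in 8.4.3 do not match, and 8.1 gives a different time point for the rates. Followed as 8.4.3 is written, the plan overstates DFS/PFS. The size is about 1 to 4.5 points at 1 year, 0.8 to 2.2 points at 2 years and 0.7 to 1.4 months on the median. These figures assume a constant hazard, medians of 8 to 36 months, and exclusion of every event in the gap.

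That is well inside the sampling error of cohorts of 12 to 36 subjects. No test, stopping rule or primary-endpoint result depends on it, and a reader should not infer that the trial's main conclusion is threatened. It is still worth correcting because the direction is known and favourable, and because the correction is mostly wording.

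**What to change.** 1. In 8.1 and 8.4.3, define time zero for DFS and PFS in the continued-therapy set as the date of the first continued-therapy dose (the first postoperative dose in operated subjects). This matches the set in 8.4.1 and the objective. It also gives a start date to subjects who continue without surgery.
2. Reconcile 8.1 with 8.4.3 so that the 1- and 2-year rates and the median share that origin and refer to stated times from it. Clarify in 2.2.2 that the year of treatment is the planned course and not an entry condition. Use one label, secondary or exploratory, throughout.
3. If a surgery-based figure is also wanted, there are two options:
   - Keep the starters and use delayed entry at first dose. No one is at risk before day 21, so the curve is conditional on being event-free at that point and should be labelled so.
   - As a sensitivity analysis, take all CR/PR/SD subjects who undergo CN/MET, count known failures before first dose as events, and censor those who leave the study at their last assessment. This answers a different question, and the censoring may be informative because these subjects leave by day 42.

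**Cost.** The main change is wording and needs no new visits. The rates and the median become slightly less favourable. The 2-year time point needs a check. In Cohort A on schedule, the ninth dose falls 8 × 42 = 336 days after the first. A year of follow-up counted from it ends on day 336 + 365 = 701 (23.0 months), so the plan should say which visit supports a 2-year rate counted from first dose.

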#### **8.4.2 Primary Analysis (or Analysis of Primary Endpoints)**

TIICs will be analyzed in pre- and post-pembrolizumab-based treatment tumor specimens. The proportion of subjects with a  $\geq 2$ -fold increase (from pre- to post-treatment) in the number of TIICs will be calculated.

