## 2 Objectives and Endpoints of the Study

### 2.1 Objectives

#### 2.1.1 Primary

- To determine the impact of pembrolizumab-based therapy on the composition, phenotype, and function of tumor-infiltrating immune cells (TIIICs) in subjects with advanced RCC undergoing CN/MET

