## 2.2 Endpoints

### 2.2.1 Primary

- The proportion of subjects with  $\geq 2$ -fold increase in the number of TICs between pre- and post-treatment tumor specimens.

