#### 3.3.1 Inclusion Criteria

1. Histologically confirmed RCC with a clear cell component.
2. Locally advanced or metastatic disease (primary intact or status post nephrectomy with recurrent disease)

3. Planned CN and/or MET.
4. Must have a tumor lesion amenable to biopsy at pre-treatment and subjects must consent to acquisition of fresh tumor specimens obtained using the following approaches:
  - i. Core biopsy
  - ii. Nephrectomy
  - iii. Metastasectomy (MET)

Note: Subjects who undergo nephrectomy or metastasectomy prior to study enrollment must still have measurable disease (RECIST 1.1) that is amenable to cytoreductive nephrectomy or metastasectomy to be eligible for study participation.

- iv. FNA specimens are not acceptable

5. Measurable disease per RECIST 1.1 as assessed by the investigator. Lesions situated in a previously irradiated area are considered measurable if progression has been demonstrated in such lesions.
6. Subject (or legally acceptable representative if applicable) must provide written informed consent for the trial.
7.  $\geq 18$  years of age on day of signing informed consent.
8. Performance status of 0 or 1 on the Eastern Cooperative Oncology Group (ECOG) Performance Scale (Appendix 1).
9. Adequate organ function as defined in Table 1; all screening labs should be performed within 10 days of treatment initiation.

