- n. Urinalysis (including microscopic exam if abnormal results are noted)
- o. Record baseline medications taken within 14 days of Cycle 1 Day 1. For stool correlative analysis, it should be noted if antibiotics were taken within 90 days before the first dose of study drug(s).
- p. To be done within 72 hours prior to the start of study drug
- q. Subjects with an R0 resection (NED, margins negative) or R1 resection (microscopic disease, margins positive) will continue receiving their assigned pembrolizumab-based therapy for up to 9 cycles or until disease progression, death, unacceptable toxicity, or withdrawal of consent, whichever occurs first. They will then enter the 1-Year Follow-Up Period.
- r. Subjects with an R2 resection (macroscopic disease after surgery), or who had a pre-operative CR but did not undergo CN, will continue receiving their assigned pembrolizumab-based therapy for up to 18 cycles or until disease progression, death, unacceptable toxicity, or withdrawal of consent, whichever occurs first. They will then enter the 1-Year Follow-Up Period.
- s. Record height at screening only
- t. Newly obtained tissue will be a fresh biopsy of primary or metastatic lesion at study baseline and must be collected from all enrolled subjects. Archival tissues will be prior tissues from primary or metastatic lesions that were originally obtained prior to study consent (where available).
- u. Subject may be consented for core tumor biopsies if CN and/or MET cannot be performed following preoperative pembrolizumab-based therapy. See section 6.1.2.4 for details.
- v. The first dose of study treatment following CN/MET may be no sooner than 3 weeks and no later than 6 weeks following surgery, to allow for postoperative recovery (adequate wound healing and recovery from any postoperative complications) as assessed by the treating surgeon. Subjects who cannot resume therapy within 42 days for any reason will discontinue study participation
- w. The timing of the End of Treatment, Safety Follow-Up and every 12 week visits during the 1-Year Follow-Up Period is relative to the last dose of study drug dosing or discontinuation.

x. These specific screening laboratory assessments (CBC with Differential and Platelet Count, Comprehensive Serum Chemistry Panel, PT/INR and aPTT, T3, FT4, and TSH, urinalysis) should be performed within 10 days of treatment initiation.

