## 8 Statistical Considerations and Evaluation of Results

### 8.1 Study Endpoints

**Primary endpoint:** The proportion of subjects with  $\geq 2$ -fold increase in the number of T1ICs between baseline and CN/MET specimens.

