## 8.2 Determination of Sample Size and Accrual Rate

### 8.2.1 Sample Size and Power Estimate

For the primary objective, there will be a binary classification. A subject will be considered to have a “positive response” if there is a  $\geq 2$ -fold increase (from pre- to post-treatment) in the number of TICCs, and a “negative response” if there is  $< 2$ -fold increase.

For Cohort A, with 12 subjects, if the true response rate is 30%, the 90% confidence interval of the response rate is (8%, 52%).

For each of the combination cohorts (cohorts B and C), the expanded part will be accrued based on group sequential design. In the first stage, 12 subjects (including the 6 subjects in safety lead-in) will be accrued at the dose level decided at safety lead in. If there are one or fewer responses in these 12 subjects, the study will be stopped due to futility, and if there are 5 or more responses,

the study will be stopped due to efficacy (one-sided alpha spending =0.0004). The final decision to terminate the cohort or continue accruing after these first 12 subjects will be based on discussion amongst members of the Joint Steering Committee, which is comprised of representatives for both Merck and the Sponsor. If accrual to the cohort is continued, additional subjects will be accrued for up to 36 evaluable subjects (or up to 30 if no dose reductions occur).

The null hypothesis of a 10% response rate will be rejected if 6 or more responses are observed in 30 subjects. This design yields a one-side type I error rate of 0.05 and power of 82.3% when the true response rate is 30%. Additionally, the first 6 subjects will be considered the “safety lead-in” for each cohort. If there are  $\geq 2$  DLTs in these first 6 subjects, then dose reduction will proceed as described in Section 5.1 and an additional 6 subjects will be accrued. The 6 subjects accrued as the safety lead-in are evaluable. Therefore, a minimum of 4, and a maximum of 36 subjects will be accrued to each pembrolizumab-based combination cohort.

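### The primary endpoint is a 2-fold rise in the number of tumour-infiltrating immune cells with no denominator, assay or operational cell definition, although the paired specimens normally differ in kind

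*Combined protocol and SAP*

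**What the plan says.** The primary endpoint appears in four places, always as a number of cells. The abbreviation is spelled in several ways; I read all of them as tumour-infiltrating immune cells (TIICs).

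- Section 2.2.1: "increase in the number of TICs between pre- and post-treatment tumor specimens".
- Section 8.1: the same comparison, but "between baseline and CN/MET specimens".
- Section 8.2.1: the binary response that drives the sample size.
- Section 8.4.2: the proportion with at least a 2-fold increase "in the number of TIICs will be calculated".

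The primary objective in 2.1.1 covers the "composition, phenotype, and function of tumor-infiltrating immune cells", which does not narrow the population to be counted. Flow cytometry is named only for circulating T cells (2.2.3.2 and 8.1).

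On the specimens, a footnote to Table 7 states: "Newly obtained tissue will be a fresh biopsy of primary or metastatic lesion at study baseline and must be collected from all enrolled subjects". Inclusion criterion 4 (3.3.1) says "subjects must consent to acquisition of fresh tumor specimens obtained using the following approaches", and lists core biopsy, nephrectomy and metastasectomy. After treatment the tissue is the nephrectomy or metastasectomy (CN/MET) specimen, or a core biopsy if surgery is not feasible (1.4.1, 3.1, 6.1.2.5).

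On evaluability, 8.4.1 takes subjects with "pre- and post-pembrolizumab treatment tumor specimens that are evaluable for TICCs". The Abstract treats subjects with PR or SD who cannot have surgery as non-evaluable for the primary endpoint only when no biopsy is collected.

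For the combination cohorts, 8.2.1 and 8.3 stop for futility at 1 or fewer responses in 12 and for efficacy at 5 or more. Section 8.2.1 rejects a 10% null at 6 or more in 30.

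**The concern.** A 2-fold change is interpretable only if both counts are on the same scale. A number without a denominator rises with the amount of tissue examined, and here the two specimens are normally of different kinds. If more tissue is examined after treatment, a tumour whose immune infiltrate has not changed can be scored as a response. If less is examined, a real increase can be missed. No rule matches specimen type, amount or anatomical site across the two time points.

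The futility, efficacy and final rules for each combination cohort all use this variable, and so does the estimate for Cohort A. The 10% null is meant to be the response rate of an inactive regimen, but that rate depends on a measurement the plan has not defined.

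There is also a direct conflict over who is in the analysis. A subject with a post-treatment biopsy in place of surgery is outside the comparison in 8.1 but inside it under 2.2.1, 8.4.1 and the Abstract.

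**Working it through.** **The plan's own figures.** Inputs from 8.2.1 and 8.3: 12 then 30 subjects, stop at 1 or fewer or at 5 or more of 12, reject at 6 or more of 30, null 10%, alternative 30%. With X1 ~ Bin(12, p) and X2 ~ Bin(18, p):

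P(reject) = P(X1 >= 5) + sum over x = 2, 3, 4 of P(X1 = x) × P(X2 >= 6 − x).

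At p = 0.10: 0.0043 + 0.2301 × 0.0982 + 0.0852 × 0.2662 + 0.0213 × 0.5497 = 0.061. At p = 0.30 the same formula gives 0.870. The plan states 0.05 and 82.3%, and 0.0004 for the interim efficacy stop, where P(X1 >= 5) at 10% is 0.0043. These figures do not reproduce. That is a separate matter; below I use the cut-offs as written. The Cohort A interval does reproduce: 0.30 ± 1.645 × sqrt(0.21/12) = 8.2% to 51.8%.

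**If the no-effect rate is not 10%.** The same rule rejects with probability 0.25 at 15%, 0.51 at 20% and 0.73 at 25%.

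**How unequal tissue moves that rate (illustration, not from the documents).** Assume that density is unchanged, that the second specimen has A times the tissue examined in every subject, and that the log2 ratio of the two counts is normal with mean log2(A) and standard deviation SD. A 2-fold rise is a log2 ratio of at least 1, so

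false-response rate = 1 − Φ((1 − log2 A)/SD).

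SD = 0.78 is chosen because it gives 1 − Φ(1/0.78) = 10% at equal tissue. At A = 1.5, (1 − 0.585)/0.78 = 0.532, and 1 − Φ(0.532) = 0.297.

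| A | SD | False-response rate | P(reject), no drug effect |
|---|---|---|---|
| 1 | 0.78 | 10% | 0.061 |
| 1.25 | 0.78 | 19% | 0.47 |
| 1.5 | 0.78 | 30% | 0.86 |
| 2 | 0.78 | 50% | 0.997 |
| 1.5 | 0.5 | 20% | 0.52 |
| 1.5 | 1.0 | 34% | 0.93 |

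At A = 2 the rate is 50% whatever the SD, because 1 − log2(2) = 0. Part of the SD = 1.0 result is noise rather than tissue: at equal tissue that SD already gives a rate of 16% and a rejection probability of 0.29. With SD = 0.5 and equal tissue the rate is 2.3% and rejection is practically nil, so there the whole of the 0.52 comes from the tissue ratio.

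**The other direction.** A subject with surgical tissue at baseline and a core biopsy afterwards may have A below 1. At A = 0.5, density would have to rise 2/0.5 = 4-fold to be scored as a 2-fold rise.

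**Specimen wording side by side.** Section 8.1 compares baseline with CN/MET tissue only. Section 2.2.1 says post-treatment specimens, 8.4.1 says post-treatment specimens that are evaluable, and the Abstract excludes only those with no biopsy. The last three agree; 8.1 stands alone.

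**The case against.** The strongest reply is that the text says number without saying how it is obtained. The plan refers tissue collection to a Laboratory Manual (5.1.3, 6.1.2.5), correlative sample collection to a Procedure Manual (1.4.1) and further immune analyses to a procedures manual (8.1, under exploratory endpoints). None was available for this review, and any of them might normalise the count. This stands as a limit: the documents do not show that the laboratory will use an unadjusted count. It does not remove the point, because no section assigns the definition of the primary endpoint to a manual.

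A reader might also infer that response could be claimed on whichever cell type doubles. The documents do not support that. The endpoint is worded as one total, no section lets any one of several subsets qualify a subject, and subsets appear only under exploratory endpoints. What is open is narrower: which cells the laboratory will count as TIICs.

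A reader might further assume a very large tissue ratio, such as core against whole nephrectomy. The documents give no amounts and do not say that all of a larger specimen is examined, so only modest, labelled ratios are used here.

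Finally, at 12 subjects the final decision rests with the Joint Steering Committee, and at 30 the text gives a hypothesis test rather than a go/no-go rule. The endpoint informs these decisions without dictating them.

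**Conclusion.** The point holds. As written, the primary endpoint lacks a denominator, an assay and an operational cell definition, and it compares specimens that normally differ in kind. Applied literally, it gives a biased primary result whose direction and size depend on the tissue examined. The 10% null has no stated basis and need not be the no-effect rate.

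The size cannot be derived from the documents. With an SD of 0.78 and 1.25 to 2 times more tissue, the chance of rejecting with no drug effect runs from 0.47 to 0.997; at 1.5 times more tissue and SD 0.5 to 1.0 it runs from 0.52 to 0.93. These figures rest on an assumed SD, a tissue ratio common to all subjects and unchanged density. In practice the ratio would vary by subject and could fall below 1.

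The conflict between 8.1 and the other sections over the post-treatment specimen needs no assumption. It is a wording mismatch, but it changes who is evaluable.

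**What to change.** - In 2.2.1, 8.1, 8.2.1 and 8.4.2, define response as at least a 2-fold increase in TIIC density: cells per mm2 of viable tumour or, if the assay is run on dissociated tissue, the fraction of viable cells. Choose one of the two according to the assay.
- State one TIIC definition and use the same assay on both specimens, both fixed before the primary data are analysed. If a manual already contains this, copy it into the protocol.
- Use the 8.4.1 specimen wording in 8.1.
- Report a sensitivity analysis limited to pairs from the same lesion site, since density does not remove differences between primary and metastatic lesions.

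The cost is wording in four places and one added analysis. Pairs without enough viable tissue for a density become non-evaluable, and 8.2.2 allows up to 2 replacements for that reason. The documents do not show how samples already collected were processed, so the sponsor should confirm that a density or fraction can still be obtained from them.
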